2.6.3.9 Analytical strategy for the exploratory analysis: subgroup analysis

To help us understand how the intervention might work differently for different subgroups, we will repeat the same analysis as specified in the primary analysis above for primary outcomes, for each of the following subgroups separately:

Subgroups of interest	Cut-off criteria	Expected proportion of the sample
People who live in the most deprived areas	Participants will be categorised as living in the most deprived areas if their post code corresponds to Index of Multiple Deprivation (IMD) ≤ 2 (top 20% most deprived)	51.3% (source: Wolverhampton deprivation status)
Ethnicity	5 GSS macro groups [White / Mixed or multiple ethnic groups / Asian or Asian British / Black or African or Caribbean or Black British / Other ethnic group]	White: 68%; Asian: 18%; Black: 7%; Mixed: 5% Others: 2% (source: Wolverhampton's census statistics)
Sex	Male; female; prefer not to say	~ 50% males (source: Wolverhampton's census statistics)
Age	Age ≤ median age of the sample; Age > median age of the sample	~ 50% vs. 50%
Baseline diet	Self-reported daily consumption of fruit and veggie ≥ 3 portions self-reported daily consumption of fruit and veggie < 3 portions	~ 62% (≥ 3 portions) vs. 38% (< 3 portions) ⁶⁰

Table 12. Subgroups

⁶⁰ According to the Health Survey for England, on average, adults consume 3.7 portions per day, and given that the standard deviation is 2.4 portions per day, 3 portions/day is about 0.3 SD below the average, corresponding to 38% of the population assuming the distribution of fruit and vegetable consumption is normal.

active) MVPA < 30 mins / week (inactive)	~ 73% (active) vs. 27% (inactive), according to the Sport England Active Lives Survey
---------------------------------------------	-------------------------------------------------------------------------------------------------------

2.6.3.10 Analytical strategy for the exploratory analysis: Motivation to change and unintended consequences

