- baseline overweight/obesity status (BMI ≥ 25),
- ethnicity,
- deprivation status,
- disability status (self-reported presence or absence of physical or mental health conditions or illnesses lasting or expected to last 12 months or more categorised as yes, not, prefer not to say),
- education (degree or above; professional, vocational or other work-related qualifications; no qualification; prefer not to say)
- brand of wearable (Apple watch, Fitbit, Better Health fitness tracker), Garmin, others),
- study arm (control, low incentives, medium incentives, high incentives),
- baseline MVPA, and
- baseline fruit and vegetable intake.

The cut offs for each predictor will be defined following the same criteria used in the impact evaluation (unless specified above).

Estimated coefficients and statistical testing for the predictors will provide robust insights into whether overall in-app engagement differs by any demographics and baseline behaviours. The general equation for estimating the model is as below:

(4)
$$y_{ij} = \alpha + \beta Treatment_j + \gamma_X X_{ij} + u_{ij}$$

 $u_{ij} \sim N(0, \sigma_u^2)$ for all i, j

where

- y_{ij} is the proportion of weeks in the intervention period that participant *i* within household *j* is categorised as being very active;
- *Treatment* is a categorical variable for treatment group (the categories are control group, low incentives, medium incentives and high incentives, with the control group being the reference category);
- *X_{ij}* are individual level (including age, sex, ethnicity, education, disability status, baseline obesity status, baseline fruit and vegetable intake, baseline MVPA, and brand of wearable) and family level covariates (e.g. deprivation status) we will take missing values for these covariates as separate categories rather than imputing;
- u_{ij} is an idiosyncratic error term, which is assumed to follow a Normal distribution (denoted as *N*) of zero mean and a variance of σ_u^2 .

Taken together this analysis section will help to answer following questions:

- To what extent does the app reach participants?
- What are the characteristics of people taking up the programme?
- To what extent does the app engage participants?
- What characteristics predict participants' in-app engagement for the duration of the trial?
- To what extent do incentives affect in-app engagement?

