Average cumulative value of redeemed rewards from randomisation to week 24 (in £) by subgroup	Reward partners	1 (total timespan)	80	Total and by study arm. Each respectively by deprivation status (2 groups), ethnicity (5 groups), sex (3 groups), age (2 groups), baseline F&V intake (2 groups), baseline MVPA (2 groups).

Summary descriptive statistics (e.g., averages, proportions) will be calculated using data on all metrics in Table 17 to provide an overview of in-app engagement for the entire participant sample (i.e. all participants who sign up to the app and provide in-app consent, regardless of subsequent data completeness), and split by trial arm.

Additionally, for key metrics related to continued app usage, summary statistics will also be visualised on a weekly basis across the intervention period to provide further insights about how users' behaviour changes over time.

As specified in the table above, to uncover potential differences in engagement between different population segments, **subgroup analyses will be conducted for key metrics, namely:**

- Average number of PA challenges completed from randomisation to week 24
- Average number of diet challenges completed from randomisation to week 24
- Average cumulative number of points earned (**both verified and unverified**) from randomisation to week 24
- Average cumulative value of redeemed rewards from randomisation to week 24

The characteristics and cut offs used for these subgroup analyses will be the same as those employed as part of the impact evaluation.

We will also conduct a regression analysis to identify the factors predicting the cumulative number of points earned from randomisation to week 24, which is used to estimate users' success rate at selecting and completing diet and physical activity challenges. The factors explored in the regression will include age, sex, baseline obesity status (BMI \ge 25), ethnicity, deprivation status, disability status, education, brand of wearable, treatment arm (control, low incentives, medium incentives, high incentives), baseline MVPA, and baseline fruit and vegetable intake. The cut offs for each predictor will be defined following the same criteria used in the impact evaluation (unless specified above).

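### The two engagement regressions split age, BMI, baseline activity and baseline fruit and vegetable intake into two groups although finer values are held, losing shape and some precision for the predictors they test

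*Protocol*

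**What the plan says.** Protocol 4.2.2 regresses the share of weeks in which a participant is very active on study arm and a list of characteristics (equation 4). Protocol 4.2.3 does the same for cumulative points earned (equation 5). Both sections say that the estimated coefficients and their tests will show whether engagement differs by demographics and baseline behaviours. Section 4.2 presents this as the final quantitative plan.

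The coding rule for equation (4) is "The cut offs for each predictor will be defined following the same criteria used in the impact evaluation (unless specified above". It is repeated for equation (5): "cut offs for each predictor will be defined following the same criteria used in the impact evaluation (unless specified above".

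The impact-evaluation cut-offs are in Table 12 (2.6.3.9):

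- **Age:** "Age ≤ median age of the sample; Age > median age of the sample".
- **Baseline fruit and vegetables:** split at 3 portions a day, expected "62% (≥ 3 portions) vs. 38% (< 3 portions".
- **Baseline MVPA:** split at 30 minutes a week, expected "73% (active) vs. 27% (inactive".

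Two predictors are defined in the list in 4.2.2 itself: "baseline overweight/obesity status (BMI ≥ 25" and "education (degree or above; professional, vocational or other work-related qualifications; no qualification; prefer not to say".

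Tables 16 and 17 likewise give two groups each for age, fruit and vegetables, and MVPA. Date of birth, height and weight are mandatory at registration (2.2.2.3). MVPA is recorded in minutes per day and Intake24 fruit and vegetable intake in grams per day (Table 3).

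**The concern.** Table 12 was drawn up to report treatment effects in subgroups. In equations (4) and (5) the same cut-offs become the coding of the very variables under test. A two-level split treats everyone on one side as identical. It cannot show a curved relation, such as low engagement at both ends of the age range. It also weakens the test of a graded relation. For age, the contrast depends on the median of whoever happens to be recruited, so it cannot be carried over to another rollout.

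The primary models in 2.6.3.5 do not do this. They enter the baseline outcome as a value, equation (1) adds a missing-value indicator for it, and no cut-off is stated for age or BMI. At stake is how well the process evaluation can describe who engages.

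**Working it through.** **1. The plan's own split figure.** A footnote to Table 12 derives the fruit and vegetable split from a mean of 3.7 and an SD of 2.4 portions: "3 portions/day is about 0.3 SD below the average, corresponding to 38% of the population assuming the distribution of fruit and vegetable consumption is normal". Check: (3 − 3.7)/2.4 = −0.292, and Φ(−0.292) = 38.5%; with the rounded −0.3 it is 38.2%. The stated 38% is reproduced.

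**2. Information kept after a split.** The protocol gives no figure for this. If a predictor is normal, its effect is linear, and it is cut so that a proportion p lies on one side, the share of information kept is the squared correlation between the predictor and its indicator:

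kept = φ(z_p)² / [p(1 − p)]

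The proportions come from Table 12. For BMI they come from a footnote to Table 5, which gives 69% overweight or obese among existing app users and 70% in Wolverhampton.

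| Predictor | p | Kept | Lost | Equivalent n out of 15,500 |
|---|---|---|---|---|
| Age | 0.50 | 0.637 | 36.3% | 9,868 |
| Fruit and vegetables | 0.38 | 0.615 | 38.5% | 9,538 |
| BMI | 0.69–0.70 | 0.582–0.576 | 41.8–42.4% | 9,019–8,923 |
| MVPA | 0.27 | 0.555 | 44.5% | 8,597 |

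**3. Sensitivity to the normal assumption.** The protocol assumes normality only for fruit and vegetables. By simulation:

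- Uniform age loses 25%.
- Gamma fruit and vegetable intake with the stated mean and SD loses 46%.
- Mildly skewed BMI (lognormal, 70% at or above 25) loses 48–52%.
- Raw MVPA cannot be normal on the protocol's figures. The cut is 30/7 = 4.29 min/day. An SD of 26 (2.4.2.1) with 27% below the cut implies a mean of 20.2, which puts 22% of users below zero. Gamma or lognormal MVPA matching those two figures loses about 79–90% on the raw scale. If the effect is linear in log MVPA (lognormal case), the loss is 44.5%.

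**4. What this means at the trial's size.** Table 6 expects about 15,500 randomised. With two-sided 5% significance, 80% power and independent participants, the smallest detectable partial correlation is (1.960 + 0.842)/√15,500 = 0.0225 for a continuous term. After the split it is 0.0225/√0.637 = 0.028 (age) to 0.0225/√0.555 = 0.030 (MVPA).

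An association with exactly 80% power on the continuous scale would have 61% (age) to 55% (MVPA) power after splitting. That describes only effects at the edge of detection. At a partial correlation of 0.05, under the worst split, 0.05 × 124.5 × 0.745 = 4.64; 4.64 − 1.96 = 2.68, so power is about 99.6%.

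Household clustering reduces the effective n. With n as low as 4,200, the detectable partial correlation would be 0.043 continuous and 0.054–0.058 after splitting.

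**The case against.** The strongest defence is that the grouping is deliberate. Sections 4.2.1 and 4.2.3 align the process evaluation with the impact-evaluation subgroups, so each regression contrast matches a row of the descriptive tables and is easy for the commissioner to read. The coding is fixed in advance, and the protocol does not contradict itself here. All of that stands: this is an improvement to a design choice, not the correction of an error.

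Two practical points also stand. Table 12 defines fruit and vegetables as self-reported portions. A food frequency questionnaire is collected at baseline beside Intake24, so a switch to grams per day could change the data source. A footnote to 2.2.3 says that exercise minutes and heart rate are not required during baseline, so baseline MVPA may be absent for some participants.

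A reader might infer more than the documents support:

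- **That 36–45% of the information is lost as a fact of this plan.** The figure is a benchmark for normal predictors with linear effects, and it does not apply to education.
- **That the regressions become underpowered.** The 55–61% figures refer to an effect chosen to sit at 80% power; only small associations are at risk.
- **That the incentive effect is confounded by the coding.** Study arm is randomised, and the other coefficients are presented as predictors, not causes.
- **That about 70% of the sample would be reported as obese.** The label does shift from overweight/obesity to obesity status within 4.2.2 and again in 4.2.3, but the threshold of 25 is printed in both predictor lists, and the 70% describes Wolverhampton, not the trial sample.
- **That people with school qualifications only are certainly misclassified.** The list in 4.2.2 names no such level, but the in-app answer options are not shown, so this cannot be settled.

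**Conclusion.** The point holds as a modest improvement. Both regressions use two-level coding for four predictors whose finer values are collected, in models meant to test those predictors. The benchmark loss is about 36% (age), 38% (fruit and vegetables), 42% (BMI) and 45% (MVPA). It rests on normality, linearity and the protocol's expected split proportions. It could be as low as 25% for age and well above 45% for skewed MVPA.

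At about 15,500 randomised, the practical loss of power is small. The main cost is that the shape of each relation cannot be seen and that the age contrast is tied to the recruited median. The primary analysis and the randomised comparison of arms are not affected. The BMI label and the education list are minor wording points and do not carry the finding.

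**What to change.** In equations (4) and (5), enter age, baseline BMI, baseline MVPA and baseline fruit and vegetable intake as continuous terms, each with a spline to allow curvature. Take fruit and vegetable intake from the same source that Table 12 uses, and name that source. Where a baseline value is absent, add a missing indicator, as equation (1) already does. Report predicted engagement at chosen values of each predictor. Keep the Table 12 cut-offs for the descriptive subgroup tables.

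Two wording changes go with this. Call BMI of 25 or more overweight or obesity throughout, and state where school-level qualifications fall in the education grouping, using the answers already collected.

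The cost is a change of text and code, with no new data. The downside is that coefficients are less direct to read and no longer map one-to-one onto the subgroup tables; the predicted values largely make up for the first.

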4.2.3. Engagement with the intervention and mechanisms of action

As indicated in the ToC, beyond the initial engagement with the intervention (e.g. providing in-app consent), continued engagement with the app is critical to driving behavioural change in PA and diet activity.

This includes successful onboarding during the baseline stage, selecting and completing challenges, logging behaviours, verifying behaviours, and redeeming incentive rewards.

To explore these themes, the quantitative IPE will analyse the metrics summarised in Table 17. All data will be collected via the app or by reward providers and will be obtained from HUL. The analyses outlined in this section will also rely on HUL sharing the metrics described in Table 17 with BIT.

Table 17. Metrics underlying the 'engagement with the intervention and mechanisms of action' analysis

	Data	Number of	Number of	
Metric	source	timepoints	groups	Which groups
% of consenting participants completing their profile before randomisation (in %)	In-app data	1 (total timespan)	1	Total sample
% of consenting participants connecting the wearable device before randomisation (in %)	In-app data	1 (total timespan)	1	Total sample
% of consenting participants that are active during the "new user journey" (defined as app opened at least once every 7 days over the 30 days after randomisation) (in %)	In-app data	1 (total timespan)	5	Total and by study arm
Average daily number of hours the wearable device is worn from consent to week 24 (in N)	In-app data	1 (total timespan)	5	Total and by study arm
Average daily number of hours the wearable device is worn per week from consent to week 24, by week (in N)	In-app data	22 (weekly)	5	Total and by study arm
Average number of PA challenges selected per week from randomisation to week 24 (in N)	In-app data	1 (total timespan)	5	Total and by study arm
Average number of PA challenges successfully completed per week from randomisation to week 24 (in N)	In-app data	1 (total timespan)	5	Total and by study arm
Average number of PA challenges successfully completed per week by difficulty from randomisation to week 24 (in N)	In-app data	1 (total timespan)	5	Total and by study arm for three difficulty levels
Weekly number of PA challenges successfully completed from randomisation to week 24, by week (in N)	In-app data	22 (weekly)	5	Total and by study arm for three metrics
Average number of diet challenges selected per week from randomisation to week 24 (in N)	In-app data	1 (total timespan)	5	Total and by study arm
Average number of diet challenges successfully completed per week from randomisation to week 24 (in N)	In-app data	1 (total timespan)	5	Total and by study arm
Average number of diet challenges completed per week by difficulty from randomisation to week 24 (in N)	In-app data	1 (total timespan)	15	Total and by study arm for three difficulty levels
Weekly number of diet challenges successfully completed from randomisation to week 24, by week (in N)	In-app data	22 (weekly)	5	Total and by study arm
Total number of times each challenge has been selected	In-app data	1 (total timespan)	1	Total sample
Total number of times each reward has been selected	In-app data	1 (total timespan)	1	Total sample
Cumulative number of points per week earned (verified) from randomisation to week 24 (in N)	In-app data	1 (total timespan)	5	Total and by study arm

Cumulative number of redeemed rewards from randomisation to week 24 (in N)	Reward partners	1 (total timespan)	5	Total and by study arm
Cumulative \pounds value of redeemed rewards from randomisation to week 24 (in \pounds)	Reward partners	1 (total timespan)	5	Total and by study arm
Average number of PA challenges completed successfully per week from randomisation to week 24, by subgroup (in N)	In-app data	1 (total timespan)	80	Total and by study arm. Each respectively by deprivation status (2 groups), ethnicity (5 groups), sex (3 groups), age (2 groups), baseline F&V intake (2 groups), baseline MVPA (2 groups).
Average number of diet challenges completed per week from randomisation to week 24 (in N) by subgroup	In-app data	1 (total timespan)	80	Total and by study arm. Each respectively by deprivation status (2 groups), ethnicity (5 groups), sex (3 groups), age (2 groups), baseline F&V intake (2 groups), baseline MVPA (2 groups).
Average cumulative number of points earned from randomisation to week 24 (in N) by subgroup	In-app data	1 (total timespan)	80	Total and by study arm. Each respectively by deprivation status (2 groups), ethnicity (5 groups), sex (3 groups), age (2 groups), baseline F&V intake (2 groups), baseline MVPA (2 groups).
Average cumulative value of redeemed rewards from randomisation to week 24 (in £) by subgroup	Reward partners	1 (total timespan)	80	Total and by study arm. Each respectively by deprivation status (2 groups), ethnicity (5 groups), sex (3 groups), age (2 groups), baseline F&V intake (2 groups), baseline MVPA (2 groups).

Summary descriptive statistics (e.g., averages, proportions) will be calculated using data on all metrics in Table 17 to provide an overview of in-app engagement for the entire participant sample (i.e. all participants who sign up to the app and provide in-app consent, regardless of subsequent data completeness), and split by trial arm.

Additionally, for key metrics related to continued app usage, summary statistics will also be visualised on a weekly basis across the intervention period to provide further insights about how users' behaviour changes over time.

As specified in the table above, to uncover potential differences in engagement between different population segments, **subgroup analyses will be conducted for key metrics, namely:**

- Average number of PA challenges completed from randomisation to week 24
- Average number of diet challenges completed from randomisation to week 24
- Average cumulative number of points earned (**both verified and unverified**) from randomisation to week 24
- Average cumulative value of redeemed rewards from randomisation to week 24

The characteristics and cut offs used for these subgroup analyses will be the same as those employed as part of the impact evaluation.

We will also conduct a regression analysis to identify the factors predicting the cumulative number of points earned from randomisation to week 24, which is used to estimate users' success rate at selecting and completing diet and physical activity challenges. The factors explored in the regression will include age, sex, baseline obesity status (BMI \ge 25), ethnicity, deprivation status, disability status, education, brand of wearable, treatment arm (control, low incentives, medium incentives, high incentives), baseline MVPA, and baseline fruit and vegetable intake. The cut offs for each predictor will be defined following the same criteria used in the impact evaluation (unless specified above).

Estimated coefficients and statistical testing for the above predictors will provide robust insights into whether overall engagement with incentives differs by any demographics and baseline PA and diet behaviours. The general equation for estimating the model is similar to that of the impact evaluation:

(5)
$$y_{ij} = \alpha + \beta Treatment_j + \gamma_X X_{ij} + u_{ij}$$

 $u_{ij} \sim N(0, \sigma_u^2)$ for all i, j

where

- y_{ij} is the cumulative number of points earned (**both verified and unverified**) from randomisation to week 24 for participant *i* within household *j*;
- *Treatment* is a categorical variable for treatment group (the categories are control group, low incentives, medium incentives and high incentives, with the control group being the reference category);
- *X_{ij}* are individual level (including age, sex, ethnicity, education, disability status, baseline obesity status, baseline fruit and vegetable intake, baseline

MVPA, and brand of wearable) and family level covariates (e.g. deprivation status) - we will take missing values for these covariates as separate categories rather than imputing;

• u_{ij} is an idiosyncratic error term, which is assumed to follow a Normal distribution (denoted as *N*) of zero mean and a variance of σ_u^2 .

We will use a compound symmetry covariance structure (as is implied by the random intercepts). Linear regression will be used for continuous outcomes, and logistic regression will be used for binary outcomes.

Taken together this analysis section will help to answer following questions:

- Overall, to what extent does the intervention engage participants?
- What characteristics predict participants' engagement with the interventions?
- In what ways did users engage with specific intervention components after signing up?
- To what extent do incentives affect engagement with specific intervention components?

